2.1.2.2 Multiple assessments within visit windows

It is possible that multiple assessments of a patient fall into the same visit-window (e.g. due to unscheduled visits). All results (scheduled and unscheduled) will be displayed in applicable listings, but only one value (observed or derived) will be selected for summary statistics by visit-window.

For **quantitative variables**, the assessment closest to the target day will be selected. If more than one assessment is at the same distance to the target day, the later one will be selected. For tables displaying the worst case scenario, such as shift tables or notable abnormalities, all assessments within a visit window will be used to identify the worst (e.g. the maximum or the minimum depending on parameter).

For **qualitative variables**, the worst record is selected; it is noted that in the relevant data subsection, worst case is always well defined.

2.2 Analysis sets

All screened patients (SCR): The SCR set comprises all patients who were screened.

BE analysis set: All patients randomized to PFS (Abdomen) or AI (Abdomen) treatment arms with PK data during dosing interval starting at Week 8. Patients will be grouped by the randomized treatment. Major deviation from the randomized treatment as defined in [Table 5-5](#) and [5.6](#) will result in exclusion of patients from the primary analysis.

PK analysis set: All patients randomized to PFS (Abdomen) or PFS (Thigh) or AI (Abdomen) or AI (Thigh) treatment arms with PK data during dose administrations. Patients will be grouped by the randomized treatment.

Safety set: All patients randomized and have taken at least one dose of study drug. Patients will be grouped by the actual treatment received. If patients received study treatment different from the randomized treatment accidentally during the study, they will be analyzed according to the treatment to which they were exposed longer in duration.

2.2.1 Subgroup of interest

None specified for the purpose of clinical study report.

2.3 Patient disposition, demographics and other baseline characteristics

Patient disposition, demographics, MS disease history, [REDACTED], and MS medication history will all be summarized by treatment group based on the safety set unless specified otherwise.

2.3.1 Patient disposition

The number and percentage of patients who completed the study or prematurely discontinued study will be presented, along with the primary reason for discontinuation. Data collected on the End of Study Disposition CRF page will be used to summarize this information.

The number and percentage of patients in each analysis set will be presented. Protocol deviations will be summarized by deviation categories.

Patients exclusion from BE analysis set will be listed for all patients with reasons for exclusion (i.e. including both protocol and non-protocol deviations).

2.3.2 Background and demographic characteristics

Background characteristics include recipient demographic characteristics (gender, race and ethnicity collected on the Demography CRF), age, height, body weight, and BMI at baseline.

Derived baseline height, body weight and BMI will be presented. These variables will be summarized using frequency distributions (for categorical variables) and descriptive statistics of mean, standard deviation, minimum, median and maximum (for continuous variables).

2.3.3 MS baseline disease characteristics

MS baseline characteristics, MS disease history and MS medication history will be summarized.

MS baseline characteristics include baseline EDSS, [REDACTED]

MS disease history includes duration of MS since diagnosis (years), duration of MS since first symptom (years), number of relapses in the last 12 months prior to screening, number of relapses in the 12 to 24 months prior to screening, type of MS at study entry (i.e., RRMS or SPMS), time since onset of SPMS, and time since onset of most recent relapse (months) prior to screening.

Duration of MS since diagnosis (years) will be derived [(first dose date – MS diagnosis start date + 1)/365.25]; duration of MS since first symptom (years) will be derived as [(first dose date – first MS symptom date + 1)/365.25]; time since onset of SPMS (years) will be derived as [(first dose date – conversion to SPMS date + 1)/365.25]; and time since onset of most recent relapse (months) will be derived as [(first dose date – most recent relapse onset date + 1)/(365.25/12)]. In these calculations, partial dates if any will be imputed according to the rules specified in [Section 5.1.3.3](#).

MS medication history of previous disease-modifying drugs (coded by WHO drug dictionary) will be summarized by preferred term (PT). The number and proportion of treatment-naïve patients (i.e., patients who have not been treated with any disease-modifying drug before study enrolment) will also be presented.

2.3.4 Medical history

Medical history will be summarized. Any condition entered on the Medical History (MH) CRF will be coded using the MedDRA dictionary. The medical history will be summarized by primary system organ class (SOC) and preferred term (PT).

2.4 Treatments (study treatment, rescue medication, concomitant therapies, compliance)

All analyses in this section will be performed on the Safety set.

2.4.1 Study treatment

Patients are expected to take a total of 6 injections at Day 1, Day 7, Day 14, Day 28 (Week 4), Week 8 and Week 12. The number of injections actually taken will be summarized descriptively by treatment group.

Duration of exposure to study drug will be calculated as (last injection date – first injection date + 31 – $\sum [(j+1)^{\text{th}}$ injection date – j^{th} injection date – 31]), where j and $j+1$ refer to consecutive

injections with injection dates more than 31 days apart (as patients are scheduled to take the subcutaneous injections every 28 +/- 3 days).

Duration of exposure to study drug will be summarized descriptively by treatment group and duration category (i.e., number of patients exposed to study drug for at least 4 weeks, 8 weeks, and 12 weeks will be provided). Descriptive statistics of duration in days will also be provided by treatment group.

For each treatment group, the number of patient-years is calculated as (the sum of the number of days of exposure for all patients in the group)/365.25 and will be summarized.

Time at risk is defined as the number of days spent in the study, from first to last administration of study drug, plus the safety data cut-off of 100 days. Time at risk corresponds to the time period used for adverse event reporting on the safety set. If the corresponding last day of time at risk for AE is after the database lock date, then it will be truncated by the database lock date. Time at risk will be summarized in a similar way to duration of exposure to study drug.

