2.1 Data analysis general information

Novartis statistical and programming team will be performing the final CSR analysis as planned in this document unless otherwise specified. The Statistical Analysis System (SAS) 9.4 and/or R 15.2.1 or higher versions will be used.

Unless otherwise stated, summary tables/figures/listings will be on all patients in the respective analysis sets. Categorical data will be presented as frequencies and percentages. For continuous data, mean, standard deviations, median, 25th and 75th percentiles (optional), minimum and maximum will be presented.

The Week 12 CSR analysis cut-off date will be the Week 12 visit date or EOS date if patients drop out of the study prematurely. All data up to this date will be included in the Week 12 CSR. A complete analysis of the post-treatment safety follow-up will be provided in the Final CSR when all patients have completed Safety FU period.

For analyses of adverse events, only data up to and including the safety cutoff of 100 days (5 x 20 days takes the long half-life of ofatumumab into account) after last administration of study drug or the subject entered the Study G2399 will be considered. Therefore, observations obtained more than 100 days after last administration of study drug will be excluded from the

analyses. Nevertheless, all serious adverse events (SAE) and all deaths, regardless of the safety cut-off will be summarized.

All data (collected or derived) will be listed appropriately.

Table 2-1 provides an overview on all planned reporting.

Table 2-1 Analyses for Week 12 registration vs. Final CSR

	Week 12 registration CSR	Final CSR
PK + immunogenicity	Complete	Complete
Tables + figures of planned safety assessments ¹	Complete up to Week 12 / EOS, no reporting of assessments during safety follow-up	Complete, including all assessments during safety follow-up
Listings of planned safety assessments ²	Complete up to 12 week DBL date	Complete, including all assessments during safety follow-up
Adverse events	Up to and including the safety cutoff of 100 days after last administration of study drug or the subject entered the Study G2399 or 12 week DBL date, whatever comes first	Up to and including the safety cutoff of 100 days after last administration of study drug or the subject entered the Study G2399, whatever comes first

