2.8.1 Adverse events (AEs)

An adverse event (AE) is any untoward medical occurrence (i.e., any unfavorable and unintended sign [including abnormal laboratory findings], symptom or disease) in a patient or clinical investigation of a patient after providing written informed consent for participation in the study. That means that a patient can report AEs before having started study medication. For reporting purposes, the main focus will be on treatment emergent adverse event (TEAE), defined as any adverse event which started on or after the day of first dose of study medication.

Except for serious TEAEs and death, only TEAEs up to and including safety cut-off of 100 days after last administration of study drug will be included in the analyses. All serious TEAEs and death will be included, regardless of safety cut-off.

AEs will be reported by primary system organ class (SOC) and preferred term according to the Medical Dictionary for Regulatory Activities (MedDRA). The MedDRA version used for reporting the study will be described in a footnote.

The number and percentage of patients reporting any TEAEs (referred to as incidence of any TEAEs later) will be summarized by primary SOC, preferred term and treatment. Separate summaries will be provided for serious TEAEs, drug related TEAEs, TEAEs leading to permanent discontinuation of study drug and most common TEAEs ($\geq 2\%$ in any of the treatment groups). Additionally, incidence of any TEAEs will also be summarized by SOC, preferred term, and maximum CTCAE grade. Missing CTCAE grade will not be imputed.

If a patient reported more than one adverse event within the same primary system organ class, the patient will be counted only once with the maximum CTCAE grade at the system organ class level, where applicable.

All AEs will be presented in listings.

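### SAP 2.4.1 leaves out the cut at G2399 entry that Table 2-1 applies to adverse events, so descriptive time at risk is overstated for patients who enter G2399 within 100 days of the last dose and before lock

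*SAP*

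**What the plan says.** **Time at risk (SAP 2.4.1).** The count runs from first to last injection, and 100 days are added. One event can shorten it: if the last day at risk "for AE is after the database lock date, then it will be truncated by the database lock date". The section equates the result with the adverse-event window ("Time at risk corresponds to the time period used for adverse event reporting on the safety set") and gives its use: "Time at risk will be summarized in a similar way to duration of exposure to study drug".

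**Adverse-event window (SAP 2.1 and Table 2-1).** The text of 2.1 says that, for adverse events, only data up to 100 days "after last administration of study drug or the subject entered the Study G2399 will be considered". The adverse-event row of Table 2-1 gives an explicit earliest-of rule in each column:
- Week 12 registration CSR: 100 days after the last dose "or the subject entered the Study G2399 or 12 week DBL date, whatever comes first".
- Final CSR: 100 days after "last administration of study drug or the subject entered the Study G2399, whatever comes first".

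The row for tables and figures of planned safety assessments has no G2399 cut. Its Week 12 entry reads "Complete up to Week 12 / EOS, no reporting of assessments during safety follow-up".

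**Adverse-event section (SAP 2.8.1).** Serious events and deaths apart, "only TEAEs up to and including safety cut-off of 100 days after last administration of study drug will be included in the analyses". G2399 is not mentioned.

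**Safety follow-up (SAP 2.8.6 and 2.8.6.2).** No safety cut-off applies there. The Final CSR reports treatment-emergent events that start after the last dose.

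**The concern.** A time-at-risk summary tells the reader how long patients were observed for the events in the adverse-event tables. Under Table 2-1, a patient who has moved into G2399 contributes no further adverse events to this study. Under 2.4.1 the same patient goes on accruing days at risk, up to 100 days after the last dose or until lock. For that patient, the definition in 2.4.1 and its statement that the two periods match cannot both be true if Table 2-1 sets the period.

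This is not a rare path. Protocol 3.6 offers G2399 to all eligible patients as a direct continuation, and SAP 2.8.6.1 expects few patients to have data after stopping study drug. What is at stake is the accuracy of one descriptive safety summary, and a programmer's ability to derive it without choosing between two sections.

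**Working it through.** The plan gives no figure to reproduce, so the check is date arithmetic on the two definitions.

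**Inputs**
- 100-day addition and truncation at lock: SAP 2.4.1.
- Earliest of 100 days, G2399 entry and (Week 12 CSR) lock: Table 2-1, adverse-event row.
- Planned last dose at Week 12, Day 84: SAP 2.4.1 and Protocol Table 6-1.
- g = days from last dose to G2399 entry; L = days from last dose to the applicable lock. Neither is in the documents, so both are varied.

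**Formulas (days after the last dose)**
- End under 2.4.1: min(100, L)
- End under Table 2-1: min(100, g, L)
- Overstatement: max(0, min(100, L) - g)

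**Overstatement per patient, in days**

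| g | L of 100 or more | L = 60 | L = 28 |
|---|---|---|---|
| 0 | 100 | 60 | 28 |
| 14 | 86 | 46 | 14 |
| 28 | 72 | 32 | 0 |
| 31 | 69 | 29 | 0 |
| 56 | 44 | 4 | 0 |
| 84 | 16 | 0 | 0 |
| 100 or more | 0 | 0 | 0 |

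**Worked example.** Last dose on Day 84, days counted inclusively from Day 1, g = 28, lock not binding. SAP 2.4.1 gives 84 + 100 = 184 days. The Table 2-1 window gives 84 + 28 = 112. The difference is 72 days. Counting elapsed days instead (183 against 111) gives the same difference.

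**A bound under an assumption.** Protocol 5.5.4 sets a 28-day dosing interval with a 3-day tolerance. If that interval is kept across the roll-over, and entry is no later than the next due dose, then g is at most 28 + 3 = 31. The excess is then 69 to 100 days where lock does not bind. The G2399 schedule is not in these documents, so this is an assumption and not an estimate.

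**Can truncation at lock remove the gap?** Only when lock is on or before G2399 entry. For early patients that is unlikely. The SAP document history dates the first version, at the FPFV time point, 12-Sep-2018, and shows the Week 12 lock still pending on 18-Sep-2019. Take a patient screened on that first date (assumption), with the full 30-day screening period and a last dose on Day 84. The last dose falls about 3-Jan-2019 and 100 days later is about 13-Apr-2019, before the lock. A patient who kept receiving study drug while waiting for the extension, as Protocol 3.1 allows, has a later last dose and a smaller L.

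**The case against.** The strongest case is that Table 2-1 is presented as an overview, while 2.8.1 is the section devoted to adverse events. Its 100-day limit is the one used in 2.4.1. The prose in 2.1 mentions G2399 but gives no earliest-of rule, and goes on to exclude only observations more than 100 days after the last dose. On that view 2.4.1 matches the adverse-event section as written. In addition, 2.8.6.2 reports events after the last dose with no cut-off, so there is no single reporting period to match.

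Part of this stands. The SAP does state two windows, and 2.4.1 follows one of them, so correcting 2.4.1 alone would not be enough. The follow-up window in 2.8.6.2 also needs to be set apart. But the earliest-of rule appears in both columns of the adverse-event row, and the separate row for serious events and deaths also stops at G2399 entry. The cut is therefore deliberate, and silence in 2.8.1 does not remove it. Nor does the reference in 2.4.1 to days spent in the study supply it, because the 100 days are added regardless.

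It is also fair to object that nothing inferential depends on this. That is correct and limits the severity. A reader might infer that adverse-event rates are diluted by the extra days. The documents do not support that: events are reported as number and percentage of patients, and patient-years use days of exposure. A reader might also infer that the general safety cut-off wording in 2.1.1 and 2.8 is in conflict. Both passages defer to explicit statements elsewhere, and they also govern laboratory and vital-sign data, for which Table 2-1 states no G2399 cut.

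**Conclusion.** The inconsistency is real and minor. Time at risk under 2.4.1 is longer than the Table 2-1 adverse-event window by max(0, min(100, L) - g) days for a patient who enters G2399 within 100 days of the last dose and before the applicable lock. For all other patients the difference is zero.

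Confidence is high that the texts differ. The size is conditional, because g, L and the share of patients rolling over are not given. It would go too far to say that most patients carry 69 to 100 excess days: that range needs the dosing-interval assumption and a lock that does not bind, and nothing here supports a cohort total. The rule is the same in all four arms. No exposure-adjusted rate, patient-years of exposure or bioequivalence result changes.

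**What to change.** 1. In SAP 2.4.1, end time at risk at the earliest of last dose + 100 days, entry into G2399, and the database lock that applies to the given CSR.
2. In SAP 2.8.1, add the same G2399 cut to the sentence on non-serious events, so that it agrees with the Table 2-1 adverse-event row.
3. State that the analysis without a cut-off in 2.8.6.2 is a separate window that time at risk does not describe.
4. Leave the general cut-off wording in 2.1.1 and 2.8 as it is.

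**Cost.** The text change is small, and the G2399 entry date is already needed for Table 2-1. Reported time at risk becomes smaller. Both addenda in the document history are dated after lock, so a further post-lock addendum and re-derivation of one table may be needed. Adverse-event counts stay the same only if programming already follows Table 2-1. If 2.8.1 was followed literally, any events in the database dated after G2399 entry would drop out, and the addendum should say which rule was used.

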2.4.2 Prior, concomitant and post therapies

2.4.2.1 Concomitant medication

Records on the Prior and Concomitant Medications CRF page will be coded using the WHO drug dictionary. All medications will be classified as prior, concomitant or post study drug discontinuation medication as follows:

- Prior medications are defined as drugs taken and stopped prior to first dose of study medication.
- Concomitant medications are defined as drugs taken at least once between first dose and last dose of study medication (including those which were started prior to first dose and continued into the treatment period).
- Post-study drug discontinuation medications will be drugs started after the discontinuation of randomized study medication.

Medications will be categorized into one (and only one) of above classes based on recorded or imputed start and end dates. When incomplete or missing, dates will be imputed according to Novartis standards (details will be given in programming datasets specifications (PDS) document). If both start date and end date are completely missing and medication was not collected on the “Previous MS Disease Modifying Treatment” page, medication will be classified into concomitant medication category.

Medications in each of these 3 categories will be summarized separately by treatment group, ATC code and preferred term. ATC level 1 and level 3 (e.g., M [Musculo-skeletal system], M01A [anti-inflammatory and anti-rheumatic products, non steroids], etc.) will be used.

Data collected from the Previous MS disease modifying treatment pages or as “Injection related premedication” will not be included in this summary.

2.4.2.2 Surgical and medical procedures

Records on the surgical and medical procedures CRF page will be coded using the MedDRA dictionary. All procedures will be classified as prior, concomitant or post-study drug discontinuation procedure, in the same way as done for concomitant medications. Surgical and medical procedures in each of these 3 categories will be summarized separately by system organ class, preferred term and treatment group.

Imputation rules for start and end dates will follow the same rule as for the concomitant medications.

2.4.2.3 Injection related premedication

Injection related premedication will be identified by subcategory “Injection related premedication” in concomitant medication data set. Injection related premedication will also be summarized separately for each injection as well as cumulatively for all injections.

For injection 1 summary, the injection related premedication with either start date or end date on the same day as the first injection date will be included and summarized for each of the three protocol specified types and for each combination of the specified types (type 1+ type 2, type 1+ type 3, type 2+ type 3, type 1+ type 2+ type 3). The three protocol specified types are steroids (type 1), antihistamines (type 2) , and antipyretics/analgesics (type 3) (corresponding to “Acetaminophen” as specified in the table shell for this summary). The steroids (type 1) will be identified by category “Steroid”. The antihistamines (type 2) will be identified by ATC level 3 “antihistamines for systemic use”. The antipyretics/analgesics (type 3) will be identified by ATC level 3 “other analgesics and antipyretics” and “anti-inflammatory and anti-rheumatic products, non-steroids”. In summaries for each combination of the specified types, the number and proportion of patients who took both (or all 3) types of injection related premedication at specified injection will be provided.

The rest of the injection specific summaries or cumulatively summaries will be reported similarly.

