For the first 3 injections, additional summaries will be provided by category of injection related premedication. Specifically, 9 categories are defined as 1) no injection related premedication, 2) type 1, 3) type 2, 4) type 3, 5) type 1+ type 2, 6) type 1+ type 3, 7) type 2+ type 3, 8) type 1+ type 2+ type 3, 9) Any injection related premedication. The types 1 to 3 refer to protocol specified three types of injection related premedication as stated in [Section 2.4.2.3](#).

A separate listing for injection site reaction AEs and injection systemic reaction AEs will be provided where all reported injection related reactions (IRR) (regardless of timing) will be listed along with the corresponding injection sequence number and time to onset from the most recent injection as well as from Day 1. The listing will be sorted by injection of first occurrence of symptoms. Specifically, under the first injection, patients whose first IRR was associated with the first injection will be listed; within a patient all IRRs to all injections will be listed chronologically. Under the second injection, patients whose first IRR was associated with the second injection will be listed; similarly, within a patient all IRRs to all injections will be listed chronologically. The listing will continue with subsequent injections until all patients with IRRs are included in the listing.

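### SAP 2.4.2.3 does not count a premedication record at an injection that it spans without starting or ending on that day

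*SAP*

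**What the plan says.** Eligible records are fixed by a label: "Injection related premedication will be identified by subcategory" in the concomitant medication data (SAP 2.4.2.3). For injection 1, "the injection related premedication with either start date or end date on the same day as the first injection date will be included" and summarised by three types (steroids, antihistamines, antipyretics/analgesics) and their combinations. For the combinations, "the number and proportion of patients who took both (or all 3) types of injection related premedication at specified injection will be provided". Later injections and the cumulative tables follow by extension: "The rest of the injection specific summaries or cumulatively summaries will be reported similarly".

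SAP 2.8.1.1.1 then uses premedication as a classifier for injection reactions: "For the first 3 injections, additional summaries will be provided by category of injection related premedication". It sets out that "9 categories are defined as 1) no injection related premedication, 2) type 1, 3) type 2, 4) type 3", followed by the three pairs, the triple and finally "9) Any injection related premedication". Its link back to 2.4.2.3 is for the types: "The types 1 to 3 refer to protocol specified three types of injection related premedication as stated in" that section. It does not restate the date rule, and it does not say how the no-premedication category is derived.

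Protocol 5.5.7 places premedication 30 to 60 minutes before the injection and requires every administration to be recorded. SAP 2.4.1 expects injections on Days 1, 7, 14 and 28 and at Weeks 8 and 12.

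**The concern.** The date rule tests only the two ends of a record. A record that covers the injection day without starting or ending on it fails the test. Accepting an end date as well as a start date makes a difference only for records longer than one day, so the rule already allows for multi-day records and then omits those that straddle the injection. The first three injections are about a week apart, and a single entry covering all of them is the most plausible case.

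Nor would such a record be picked up in the general medication tables, because SAP 2.4.2.1 leaves injection-related premedication out of that summary. For other medications the same section uses an interval idea: a drug begun before the first dose and continued into treatment is concomitant.

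At stake is the descriptive table of injection reactions by premedication for injections 1 to 3. Injection-related reactions belong to a secondary objective (SAP Table 1-1). A premedicated patient placed in the no-premedication row would blur the one contrast that the table is meant to show.

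**Working it through.** The plan gives no figure to reproduce. The check applies the rule literally to example records, with injections 1, 2 and 3 on their planned Days 1, 7 and 14. The records are hypothetical.

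Rule as written: count if start = injection day or end = injection day. Interval rule: count if start <= injection day <= end.

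| Record (start to end) | Injection days covered | Counted as written | Missed |
|---|---|---|---|
| Day 1 to 1 | 1 | 1 | none |
| Day 6 to 7 | 7 | 7 | none |
| Day 7 to 8 | 7 | 7 | none |
| Day 1 to 14 | 1, 7, 14 | 1, 14 | 7 |
| Day -1 to 2 | 1 | none | 1 |
| Day 6 to 8 | 7 | none | 7 |
| Day 13 to 15 | 14 | none | 14 |

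Records with an end on the injection day are handled correctly, and only the straddling ones are lost. The interval rule counts all seven records at every injection day they cover.

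To reach the no-premedication row of 2.8.1.1.1, a patient must meet three conditions: (1) a record spans the injection day with neither end on it; (2) 2.8.1.1.1 uses the link in 2.4.2.3; (3) no other labelled record qualifies for that injection. Condition 2 is an inference. The reaction tables need some link between record and injection, and 2.4.2.3 gives the only one in the plan.

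Size, by assumption only: let u be the share of patients truly unpremedicated at an injection and s the share who meet all three conditions. The misplaced fraction of the no-premedication row is s/(u + s). With u = 10% it is 0 when s = 0, and 5/(10 + 5) = 33% when s = 5%. The documents give neither u nor s, so this shows sensitivity and is not an estimate.

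Categories: three types give 2^3 = 8 subsets, which match categories 1 to 8 one to one, and category 9 is a total row. If categories 2 to 8 are exact combinations, each patient with any of the three types sits in two categories (one combination plus category 9). If a row means at least these types, a patient with two types sits in four categories and a patient with all three sits in eight. The text does not settle which is meant.

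**The case against.** The best reply is practical. Site staff give the injections, premedication is meant to be given 30 to 60 minutes beforehand, and each administration must be recorded. Labelled records should therefore normally start on the injection day, and nothing in the documents shows that spanning records occur. This stands as a reason to expect a small effect. It does not make the rule right for the records that it misses.

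A second reply is that the interval rule trades one error for another: a Day 1 to Day 14 entry does not prove that a dose was taken on Day 7. That is true, but the present rule already credits the same entry on Day 14 from its end date alone. The point has more force for open-ended records, such as a Day 1 steroid entry never closed, which should be checked before they are counted.

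Three stronger readings are tempting and are not supported:

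- A reader might infer that every patient with a spanning record is classed as unpremedicated. That needs all three conditions above.
- A reader might infer that the premedication categories overlap. Overlap is certain only for category 9. The phrase about taking both or all three describes the combination rows in 2.4.2.3, not the single-type rows, and eight categories for eight subsets fits a partition at least as well. SAP 2.4.2.3 also mentions a table shell, not available here, that may settle it.
- A reader might infer that, if the rows did overlap, the steroid-only reaction rate would be lost. It could be recovered by subtraction. Take 100 assumed patients: 60 took all three types with 12 reactions, and 10 took steroid only with 4. The inclusive steroid row shows 70 patients and 16 reactions, and each of the two pairs with steroid, and the triple, shows 60 and 12. Steroid only is 70 - 60 - 60 + 60 = 10 patients and 16 - 12 - 12 + 12 = 4 reactions, or 40%.

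**Conclusion.** The date rule in SAP 2.4.2.3, read literally, omits a labelled premedication record at any injection that it spans without starting or ending on that day. This is a flaw in a stated rule, not a missing detail. The further step, that such a patient appears as unpremedicated in the reaction tables, is conditional on 2.8.1.1.1 sharing the link and on no other record qualifying.

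The size is unknown and probably small. The tables are descriptive, and all reported injection reactions are also listed by patient. The AUCtau and Cmax analysis does not use premedication and is unaffected. The point is a cheap improvement to a secondary safety table. The category definitions call for a clarification only.

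**What to change.** In SAP 2.4.2.3, include a labelled premedication record at an injection when start date <= injection date <= end date. Check a record with no end date against the injection before counting it. State in 2.8.1.1.1 that the same rule assigns patients to the premedication categories, including the no-premedication category.

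Optionally, state that categories 1 to 8 are exact combinations, and that category 9 is any labelled premedication. Category 9 need not equal the sum of 2 to 8, because a labelled drug outside the three type definitions belongs in 9 but in none of 2 to 8.

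The cost is a few words, one programming condition and a review of open-ended records. The downside is that a long record may be credited at an injection where that premedication was not given.
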